Patients with diagnoses of chronic back pain receiving care in facilities affiliated with the VA Ann Arbor Healthcare System and the VA Connecticut Healthcare System will be identified via DART and CPRS. Eligible patients will have back-pain-related diagnoses including back and spine conditions, and nerve compression (using ICD-9 and -10 codes corresponding to appropriate conditions) and a score of ≥ 4 (indicating moderate pain) on the 0-10 Numerical Rating Scale on at least two separate outpatient encounters in the past year. Additionally, the pain clinic at the Ann Arbor VA Hospital will be able to inform potentially eligible participants about the study via flyer. If interested, these patients will be able to call the study and then be screened for eligibility.

Screening of interested and potentially eligible patients will be conducted by medical record review and telephone interview using validated measures. Inclusion criteria include: (1) at least moderate pain-related disability as determined by a score of 5+ on the Roland Morris Disability Questionnaire at baseline; (2) at least moderate musculoskeletal pain as indicated by a pain score of ≥ 4 on the Numeric Rating Scale; (3) pain on at least half of the days of the prior six months as reported on the Chronic Graded Pain Scale; and (4) a touch-tone cell or land line phone. Exclusion criteria include: (1) active psychotic symptoms, suicidality, severe depressive symptoms (Beck Depression Inventory (BDI) score of 30+, or a PHQ-9 score of >20),

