In preparation for this study, we used Corporate Data Warehouse records for 2012 to identify patients treated in Ann Arbor and West Haven with low back pain (ICD-9 codes 724.01, 724.02, 724.03, 724.09, 724.1, 724.2, 724.3, 724.4 and 724.5) and a pain score of ≥ 4 on the 0-10 Numerical Rating Scale on at least two separate outpatient encounters. We identified 105,344 patients and estimate that we would have to recruited 3-4% at a rate of 4.4 patients per site per month to reach accrual goals. Our prior studies based on similar populations have recruited 5 to 10 Veterans with chronic pain per month per FTE recruiter. Therefore we expect no difficulty recruiting the target sample within the proposed timeframe and staffing.

D.3 Randomization

After completing baseline assessments, patients will be randomized to AI-CBT or standard telephone CBT by the research staff. The randomization sequence and opaque randomization envelopes for recruiters will be generated prior to recruitment by the study statistician using a random number generator. Analysts and the investigators will be blinded to patients' group assignment until initial outcome analyses are completed. To ensure balance across treatment arms in potential modifiers of intervention effect, randomization will be conducted within blocks defined by site (Michigan versus Connecticut) and patient age (<65 vs. ≥ 65).

D.4 Common Elements of Standard and AI-CBT

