Our primary outcome analyses are consistent with the CONSORT Statement on Reporting of Noninferiority and Equivalence Randomized Trials.⁸¹ The sample size was calculated using the Non-Inferiority Test module available in the statistical software PASS 2008. The calculation was reviewed by the study statistician, [name]. To ensure that the AI-CBT program retains a clinically acceptable effect, the non-inferiority margin was set at 2 points on the Roland Morris Disability Questionnaire (RMDQ).⁷⁴ A two point difference (or difference in reduction) in the RMDQ is considered to be a minimally clinically significant effect.⁸² The power calculation was based on a significance level of 0.025, with a power of 90%, when postulating a true difference in group means of 0 and a standard deviation of the outcome of 4.5 in both groups. Specifically, if we denote by D the true difference in mean RMDQ scores (at 12 weeks) between the

AI-CBT and standard CBT groups, with the non-inferiority margin set at 2, we plan on testing the null hypothesis $H_0: D \geq 2$ versus the alternative hypothesis $H_1: D < 2$, which amounts to a one-sided, two-sample t-test. Thus, if the null hypothesis is rejected, it can be concluded that AI-CBT is non-inferior to CBT. We will test this hypothesis at a one-sided .025 significance level based on a confidence level where we will reject the null hypothesis when the upper bound of the two-sided 95% confidence interval for D is less than 2. To ensure that the AI-CBT algorithm has as much information as possible to learn quickly how best to tailor patients' course of therapy, we will disproportionately randomize patients to the AI-CBT group in an allocation ratio of 1.37:1 for the AI-CBT: standard CBT groups, respectively. Assuming this ratio, we will have 90% power to detect non-inferiority with a total sample size of 221 patients, or 128:93. To account for a 20% drop-out rate in both groups, we will enroll 278 patients (160 in the AI-CBT group, 118 in CBT group).

D.9 Analysis

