Baseline Comparability, Reach, and Representativeness. We will examine baseline differences across groups in measures of study endpoints as well as other potential prognostic indicators, such as patients' age, comorbid diagnoses, and history of pain treatment. Any differences across groups in baseline characteristics will be controlled statistically in analyses comparing outcomes. The RE-AIM framework is a methodology for systematically considering all strengths and weaknesses of an intervention in order to better guide program planning.⁸³ To evaluate reach, we will ask patients who decline study participation whether they would be willing to provide informed consent to participate in a brief survey that identifies their reasons for declining participation and the characteristics that differentiate them from enrollees.

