Analysis of Endpoints (addressing Specific Aim 1). We will test for non-inferiority of AI-CBT compared to standard telephone CBT at 12 weeks by comparing the upper limit of the two-sided 95% confidence interval for the difference in the mean RMDQ scores, calculated as AI-CBT minus standard CBT, to the pre-set non-inferiority margin of 2 points in RMDQ and will conclude that AI-CBT is non-inferior if the upper limit is less than 2. Because intent-to-treat analysis can raise the risk of type I error in a non-inferiority trial,⁸¹ we will conduct both a per protocol and intent-to-treat analysis. The "per protocol" group assignment will be defined as completing four or more CBT sessions (either IVR or "live" sessions); however, we will revisit this definition with the Expert Panel prior to the start of the trial. We will declare AI-CBT non-inferior to standard CBT only if AI-CBT is shown to be non-inferior using both the intention-to-treat and per-protocol analysis sets. We expect that RMDQ scores will be normally distributed. If not, we will use transformations to achieve normality. We also will develop a two-level linear mixed-effects model that uses RMDQ follow-up scores at both assessment times (three and six months) as the dependent variables; treatment group, time and the treatment by time interaction as categorical explanatory variables; and baseline RMDQ score as a continuous covariate. If this model shows no significant time by group effect, we can drop the interaction term and test for the time-averaged non-inferiority of AI-CBT compared to standard CBT between 3 and 6 months. This model will also allow for adjustment for design-related factors (e.g., site and age). An unstructured variance-covariance matrix will be used to model the error variance. Secondary outcomes including pain intensity, emotional functioning, global perception of change, and quality of life will be analyzed in a manner similar to that used for the primary outcome. Analyses of all other outcomes will be conducted on an intent-to-treat basis.

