Intensity of Service Use (Specific Aim 2). We will compare service utilization by category (e.g., CBT therapist time, PCP visits, and pharmacy use) between groups. We will conduct a budget impact analysis⁸⁴ and will include the cost of the intervention (personnel, supplies, CBT therapist training, and IVR fixed/variable costs) as well as costs for specific medical care services likely to be affected. Data from CBT therapists time records will be combined with wage data from the VA Financial Management System to produce estimates of intervention-specific personnel costs. Costs associated with the use of specific medical care services, such as medications, will be obtained from the Decision Support System (DSS) files. Cost analysis will be conducted in accordance with the guidance provided by Mauskopf et al.⁸⁴ including the use of sensitivity analysis and scenarios that allow for varying assumptions about intervention uptake, compliance or component costs. All resource use and cost comparisons will be adjusted for any observed differences in baseline characteristics. Because costs of resource utilization are usually skewed, alternative modeling techniques (e.g., log-transformed costs, negative binomial regression) will be used.

Intervention Engagement and Satisfaction with Care (Specific Aim 3). As in our prior research,⁴⁹ we will conduct extensive analyses of the process of intervention delivery in both arms. We will monitor the proportion of telephone CBT sessions that are completed, and we will determine the patient and session characteristics associated with patients' reports of skill practice. Patients in the AI-CBT group will report their satisfaction with aspects of the intervention (e.g., whether it provided information useful for achieving behavioral targets), and we will assess the correlation between satisfaction ratings and measures of: intervention engagement, patients' baseline characteristics, and changes in pain-related functioning. Differential dropout across groups will be examined using Kaplan-Meier curves and survival models.

Preplanned Subgroup Analysis. Because AI-CBT will continue to learn patterns in patients' experience throughout the intervention period, we hypothesize that the second 50% of patients randomized will show

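### Free improvement: the deciding 12-week non-inferiority test names no covariates, although baseline RMDQ, site and age group are already collected

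*Combined protocol and SAP*

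**What the plan says.** **The deciding test.** Protocol D.9 and the SAP (both under Analysis of Endpoints) give this rule for the 12-week decision: "comparing the upper limit of the two-sided 95% confidence interval for the difference in the mean RMDQ scores, calculated as AI-CBT minus standard CBT", with a margin of 2. Both analysis sets must pass. Protocol D.8 and the SAP's Sample Size Rationale add that the hypothesis test is one "which amounts to a one-sided, two-sample t-test", sized with a "standard deviation of the outcome of 4.5 in both groups". None of these sections names a covariate for it.

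**What is available.** Protocol D.2 requires "a score of 5+ on the Roland Morris Disability Questionnaire at baseline", so every patient has a baseline value. Protocol D.3 and the SAP's Randomization section state that "randomization will be conducted within blocks defined by site (Michigan versus Connecticut) and patient age".

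**Where adjustment appears.**
- The Analysis of Endpoints paragraphs go on to a further mixed model of the three- and six-month scores. Baseline RMDQ is a fixed covariate there, and site and age may be added. The treatment-by-time term may be dropped if it is not significant, which leads to a time-averaged test.
- Under Baseline Comparability (protocol D.9; SAP, Definitions of the Analytical Sets), baseline differences are to be examined in the endpoint measures and in indicators such as age, comorbid diagnoses and pain treatment history. Then: "Any differences across groups in baseline characteristics will be controlled statistically in analyses comparing outcomes".
- The Aim 2 text repeats that idea for costs: "All resource use and cost comparisons will be adjusted for any observed differences in baseline characteristics".

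**The concern.** One upper confidence limit decides the trial, and it has to clear the margin twice. The baseline value of the primary outcome is usually a strong predictor of its follow-up value, and the strata were chosen as potential effect modifiers. Leaving all three out of the deciding model gives up a narrower interval that costs nothing to obtain.

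The baseline-difference rule does not settle the matter. If it covers the 12-week test, that test is no longer the two-sample t-test of the sample-size sections, and observed imbalance selects the covariates. If it does not, the test is unadjusted. A reader cannot tell from the text which model will produce the limit that is compared with 2.

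**Working it through.** **Inputs from the documents** (protocol D.8; SAP, Sample Size Rationale): margin 2, one-sided level 0.025, power 90%, true difference D = 0, SD 4.5, allocation 1.37:1, evaluable patients 128:93. Enrolment is then inflated "To account for a 20% drop-out rate in both groups"; the check uses the evaluable numbers. **Assumed:** r, the correlation of baseline with 12-week RMDQ.

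**1. The plan's own figure.** Control patients = (1 + 1/1.37) × [4.5 × (1.960 + 1.282)/2]² = 92.02, rounded up to 93. AI-CBT = 1.37 × 93 = 127.4, rounded up to 128. The total is 221, as stated.

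At 128:93 without covariates, SE = 4.5 × √(1/128 + 1/93) = 0.613. With t = 1.971 (219 df) the half-width is 1.21, so the largest observed difference that still passes is 2 − 1.21 = 0.79. Non-central t power is 90.1%. The stated size therefore agrees with an unadjusted test and SD 4.5.

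**2. Adjusted test, same patients.** Residual SD = 4.5 × √(1 − r²), with 3 df removed for baseline RMDQ, site and age group. Only baseline RMDQ is credited with a gain; site and age are counted as explaining nothing.

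| r | Residual SD | Half-width | Largest passing difference | Power, D = 0 | Power, D = 0.5 |
|---|---|---|---|---|---|
| unadjusted | 4.50 | 1.21 | 0.79 | 90.1% | 68% |
| 0.1 | 4.48 | 1.20 | 0.80 | 90.4% | 69% |
| 0.2 | 4.41 | 1.18 | 0.82 | 91.2% | 70% |
| 0.3 | 4.29 | 1.15 | 0.85 | 92.6% | 72% |
| 0.5 | 3.90 | 1.05 | 0.95 | 96.3% | 80% |
| 0.7 | 3.21 | 0.86 | 1.14 | 99.5% | 93% |

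At r = 0 the three lost df cost nothing visible (still 90.1%).

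**3. If 4.5 is the SD of change** (equal SDs at both times assumed). The 12-week SD is 4.5/√(2(1 − r)), and the adjusted residual SD is 4.5 × √((1 + r)/2).

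| r | 12-week SD | Unadjusted power, D = 0 | Residual SD | Adjusted power, D = 0 |
|---|---|---|---|---|
| 0.3 | 3.80 | 97.0% | 3.63 | 98.1% |
| 0.5 | 4.50 | 90.1% | 3.90 | 96.3% |
| 0.7 | 5.81 | 71.1% | 4.15 | 94.1% |

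**4. If 4.5 is already a residual SD,** the adjusted test has the 90.1% of step 1, so there is no gain over the stated calculation.

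**The case against.** The strongest reply is that the plan already adjusts. The baseline-difference rule does say where to look: endpoint measures, which include baseline RMDQ, and several named indicators. It applies to analyses that compare outcomes, and it stands directly before the Aim 1 analysis. Taken literally, any non-zero difference is controlled. Two arm means almost never coincide, so baseline RMDQ would nearly always enter and the gain in the table would already be secured. Repeating the rule for Aim 2 is no evidence that it stops short of Aim 1. The t-test wording sits in the sample-size sections. And the mixed model in the same paragraph can supply an adjusted 12-week contrast.

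Much of this stands. It would be wrong to infer that the plan ignores baseline RMDQ, or that it names no variables. What remains is that the rule has no threshold, an open list and no named model, and does not fit the stated t-test; and that the mixed model is not named as the deciding analysis. A rule triggered by imbalance is not a substitute for fixed adjustment of the test that decides the trial.

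It is also fair that the size of the gain is conditional. The RMDQ entry threshold may narrow the baseline range and lower r; at r = 0.1 or 0.2 the gain in power at D = 0 is about one point or less.

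**Conclusion.** The point holds as a free improvement. As described, the deciding test uses no covariates, and prespecified adjustment for variables already collected would narrow its interval. With 4.5 read as the SD of the 12-week score, which is the plain sense of the text, power at D = 0 rises from 90.1% to between 90.4% (r = 0.1) and 99.5% (r = 0.7). The half-width falls from 1.21 to between 1.20 and 0.86. The benefit is modest at r of 0.3 or below. It matters more if AI-CBT is in truth slightly worse: at D = 0.5, power goes from 68% to 80% at r = 0.5. All of this rests on an assumed r and on linear adjustment at 128:93; the per-protocol set may be smaller.

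A reader might infer that the trial is underpowered or the test invalid. The documents do not support that: 221 patients reproduces and gives the stated 90% on the stated inputs. Nor is there a basis here for claiming that the baseline-difference rule inflates type I error; the objection is only that it leaves the deciding model undefined.

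**What to change.** **Analysis of Endpoints (protocol D.9 and SAP).** Name one primary analysis for both the intention-to-treat and per-protocol sets: the 12-week (three-month) treatment contrast from the planned mixed model, adjusted for baseline RMDQ, site and age stratum. Keep treatment-by-time, and a baseline-by-time term, whatever their p-values. Compare the contrast's upper 95% limit with 2. Keep the unadjusted difference in means as a sensitivity analysis and the time-averaged three-to-six-month test as secondary.

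**Baseline Comparability (protocol D.9 and SAP).** State that the baseline-difference rule applies to sensitivity analyses and does not alter the deciding test.

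**Cost.** No extra patients, visits or data, and the sample size stays as it is. The edit does more than relabel: it adds one model term, makes site and age mandatory, and bars dropping the interaction from the primary analysis. One further sentence should say how this model fits with the multiple imputation described under Approach to Missing Data. All of it should be fixed before group assignments are unblinded.

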Our primary outcome analyses are consistent with the CONSORT Statement on Reporting of Noninferiority and Equivalence Randomized Trials.⁸¹ The sample size was calculated using the Non-Inferiority Test module available in the statistical software PASS 2008. The calculation was reviewed by the study statistician, [name]. To ensure that the AI-CBT program retains a clinically acceptable effect, the non-inferiority margin was set at 2 points on the Roland Morris Disability Questionnaire (RMDQ).⁷⁴ A two point difference (or difference in reduction) in the RMDQ is considered to be a minimally clinically significant effect.⁸² The power calculation was based on a significance level of 0.025, with a power of 90%, when postulating a true difference in group means of 0 and a standard deviation of the outcome of 4.5 in both groups. Specifically, if we denote by D the true difference in mean RMDQ scores (at 12 weeks) between the AI-CBT and standard CBT groups, with the non-inferiority margin set at 2, we plan on testing the null hypothesis $H_0: D \geq 2$ versus the alternative hypothesis $H_1: D < 2$, which amounts to a one-sided, two-sample t-test. Thus, if the null hypothesis is rejected, it can be concluded that AI-CBT is non-inferior to CBT. We will test this hypothesis at a one-sided .025 significance level based on a confidence level where we will reject the null hypothesis when the upper bound of the two-sided 95% confidence interval for D is less than 2. To ensure that the AI-CBT algorithm has as much information as possible to learn quickly how best to tailor patients’ course of therapy, we will disproportionately randomize patients to the AI-CBT group in an allocation ratio of 1.37:1 for the AI-CBT: standard CBT groups, respectively. Assuming this ratio, we will have 90% power to detect non-inferiority with a total sample size of 221 patients, or 128:93. To account for a 20% drop-out rate in both groups, we will enroll 277 patients (160 in the AI-CBT group, 117 in CBT group).

Randomization

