We will examine the distribution of all study variables to assess extreme values, missing data, variances, skewness, and type of distribution. Preliminary analyses will examine the distributions of variables to assess deviations from normality and other deviations from assumptions of the planned statistical analyses. Outliers will be corrected. Transformations of the data will be conducted if appropriate to obtain normality of residuals.

Definitions of the Analytical Sets

Baseline Comparability, Reach, and Representativeness. We will examine baseline differences across

groups in measures of study endpoints as well as other potential prognostic indicators, such as patients' age, comorbid diagnoses, and history of pain treatment. Any differences across groups in baseline characteristics will be controlled statistically in analyses comparing outcomes. The RE-AIM framework is a methodology for systematically considering all strengths and weaknesses of an intervention in order to better guide program planning.⁸³ To evaluate reach, we will ask patients who decline study participation whether they would be willing to provide informed consent to participate in a brief survey that identifies their reasons for declining participation and the characteristics that differentiate them from enrollees.

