Analysis of Endpoints (addressing Specific Aim 1). We will test for non-inferiority of AI-CBT compared to standard telephone CBT at 12 weeks by comparing the upper limit of the two-sided 95% confidence interval for the difference in the mean RMDQ scores, calculated as AI-CBT minus standard CBT, to the pre-set non-inferiority margin of 2 points in RMDQ and will conclude that AI-CBT is non-inferior if the upper limit is less than 2. Because intent-to-treat analysis can raise the risk of type I error in a non-inferiority trial,⁸¹ we will conduct both a per protocol and intent-to-treat analysis. The "per protocol" group assignment will be defined as completing four or more CBT sessions (either IVR or "live" sessions); however, we will revisit this definition with the Expert Panel prior to the start of the trial. We will declare AI-CBT non-inferior to standard CBT only if AI-CBT is shown to be non-inferior using both the intention-to-treat and per-protocol analysis sets. We expect that RMDQ scores will be normally distributed. If not, we will use transformations to achieve normality. We also will develop a two-level linear mixed-effects model that uses RMDQ follow-up scores at both assessment times (three and six months) as the dependent variables; treatment group, time and the treatment by time interaction as categorical explanatory variables; and baseline RMDQ score as a continuous covariate. If this model shows no significant time by group effect, we can drop the interaction term and test for the time-averaged non-inferiority of AI-CBT compared to standard CBT between 3 and 6 months. This model will also allow for adjustment for design-related factors (e.g., site and age). An unstructured variance-covariance matrix will be used to model the error variance. Secondary outcomes including pain intensity, emotional functioning, global perception of change, and quality of life will be analyzed in a manner similar to that used for the primary outcome. Analyses of all other outcomes will be conducted on an intent-to-treat basis.

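### If RMDQ is transformed for non-normality, the primary non-inferiority test has no pre-set margin, because the 2-point margin exists only on the raw scale

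*Combined protocol and SAP*

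**What the plan says.** **Raw-scale rule.** Protocol D.8 and the SAP's Sample Size Rationale put every element of the primary test in RMDQ points.

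- Margin: "the non-inferiority margin was set at 2 points on the Roland Morris Disability Questionnaire (RMDQ").
- Estimand: "we denote by D the true difference in mean RMDQ scores (at 12 weeks").
- Variability: "a standard deviation of the outcome of 4.5 in both groups".
- Hypotheses: H0: D ≥ 2 against H1: D < 2.

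Protocol D.9 and the SAP's Analysis of Endpoints carry this into the success rule. The upper limit of the two-sided 95% interval for AI-CBT minus standard CBT must fall below 2, in both the intention-to-treat and per-protocol sets.

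**Transformation clause.** Soon after that rule, in the same paragraph of both documents, the plan says it expects normal RMDQ scores and continues: "If not, we will use transformations to achieve normality". The SAP section Methods for Dealing with Data Transformations adds a general allowance: "Transformations of the data will be conducted if appropriate to obtain normality of residuals". The triggers differ slightly, since one refers to scores and the other to residuals. Neither has a threshold.

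**Second non-inferiority test.** The mixed model over both follow-up times may be used to "test for the time-averaged non-inferiority of AI-CBT compared to standard CBT between 3 and 6 months". The general allowance would reach this test too.

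**Blinding.** D.3 and the SAP's Randomization section keep analysts and investigators blinded to group until the initial outcome analyses are done.

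**The concern.** A non-inferiority conclusion depends on its margin, and a margin belongs to a scale. The plan justifies 2 points as a minimally clinically significant difference in RMDQ. Once scores are transformed, the estimated quantity is a difference in mean transformed scores. That is not D, and in general an interval for it cannot be turned back into an interval for a difference in raw means.

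To use the success rule on that branch, someone must decide what 2 RMDQ points become on the new scale. The answer depends on the transformation, on the control-arm level and distribution, and on how the conversion is done. The plan fixes none of these, so the choice would be made after data collection, in a trial whose main claim is non-inferiority.

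The clause is also directive for RMDQ: it says what will be done if scores are not normal. A contingency written into the primary analysis should lead to a usable test when it is followed.

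**Working it through.** **1. Reproduce the plan on raw scores.** Inputs from D.8: margin 2, SD 4.5, true difference 0, one-sided 0.025, power 90%, ratio 1.37.

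- Control n = (1 + 1/1.37) × (1.960 + 1.282)² × 4.5² / 2² ≈ 1.730 × 10.51 × 5.06 ≈ 92.0, taken up to 93.
- AI-CBT n = 1.37 × 93 = 127.4, taken up to 128. Total 221, as stated.
- Standard error at 128:93 = 4.5 × √(1/128 + 1/93) = 0.613. Non-centrality = 2/0.613 = 3.26. Noncentral-t power on 219 degrees of freedom is 90.1%.

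The raw-scale design is sound.

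**2. Convert 2 points to another scale.** The documents give no 12-week mean and name no transformation, so what follows is illustration. Assumptions: square root; scores from 0 to 24 following a beta-binomial distribution; SD 4.5 in both arms (as planned); control mean c from 5 to 12. Three reasonable conversions are:

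- (a) the difference in mean √score between populations with means c + 2 and c;
- (b) plug-in, √(c + 2) − √c; for example, at c = 5, √7 − √5 = 2.646 − 2.236 = 0.41;
- (c) the average of √(y + 2) − √y over control scores y.

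| Control mean | (a) mean √ | (b) plug-in | (c) add 2 |
|---|---|---|---|
| 5 | 0.54 | 0.41 | 0.59 |
| 8 | 0.38 | 0.33 | 0.39 |
| 10 | 0.33 | 0.30 | 0.33 |
| 12 | 0.29 | 0.28 | 0.30 |

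The margin moves with the control mean. At a low mean it also depends heavily on the conversion. The choice of transformation matters as well: the plug-in on log(score + 1) at mean 5 is ln(8/6) = 0.29.

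**3. Effect on the test where a square root is a natural choice.** At control mean 5 the assumed scores are clearly right-skewed. Simulated trials with 128 and 93 patients, upper 95% limit compared with the margin:

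| Analysis at control mean 5 | Power, D = 0 | False non-inferiority, D = 2 |
|---|---|---|
| Raw scores, margin 2 | about 90% | about 2.5% |
| √, conversion (a) | about 94% | about 2.9% |
| √, conversion (b) | about 75–77% | about 0.2–0.3% |
| √, conversion (c) | about 99% | about 2.7% |

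For (b), 75% uses the true control mean and 77% the observed one. The spread comes from the choice of conversion; it is not a cost of transforming as such.

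**4. Is the transformation needed?** Over control means 5 to 12 under the same assumptions, raw scores give:

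- pooled t: power about 90%, false non-inferiority 2.3–2.5%;
- unequal-variance (Welch) t: power 90–91%, false non-inferiority 2.2–2.5%.

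At these sample sizes, an interval for a difference in raw means does not need normal scores.

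**The case against.** **The plan expects normality, so the branch may never be used.** This stands as a limit: the defect is conditional. The branch is not remote, however. RMDQ is a discrete, bounded score and no normality threshold is set. Under the assumptions above, a Shapiro–Wilk test on 221 such scores rejects in more than 60% of samples even at control mean 12, where the distribution is symmetric.

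**Blinded analysts could fix the conversion before unblinding.** This also stands in part. Blinding limits bias in the choice, but it does not make the margin pre-set or say which conversion is right.

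**A transformed analysis could have more power.** True in skewed cases: about 94% or 99% for two of the conversions at control mean 5, against about 90% on raw scores. So it cannot be said that raw scores never lose power. What they keep is the planned power, the planned error and the planned estimand.

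**Stronger readings to avoid.**

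- A reader might infer that the number 2 would be carried over unchanged to a square-root or log scale. The documents tie it to RMDQ points throughout, and nothing suggests this would be done.
- A reader might infer that transforming inflates the error rate. With conversion (a) fixed for an assumed control mean of 10 (0.33), false non-inferiority is 5.6–5.8% if the true mean is 12, and power is 77–78% if it is 8. But at means 8, 10 and 12 the square root takes skewness from 0.44, 0.20 and 0.00 to −0.47, −0.52 and −0.59. It would not improve normality there, so an analyst following the plan would have little reason to choose it. The conclusion does not rest on these figures.
- A reader might infer that the sample size or the raw-scale rule is faulty. Both are sound.

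**Conclusion.** The point holds as a conditional gap in the primary analysis. The plan directs a transformation of RMDQ if scores are not normal, but supplies a margin, hypotheses and success rule only for raw RMDQ means. If the direction is followed, the test is no longer a test of H0: D ≥ 2 and its margin has to be constructed after data collection.

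The size depends on figures the plan does not give. Under the stated assumptions at control mean 5, the margin ranges from 0.41 to 0.59 and power from about 75–77% to 99%, solely through the choice of conversion. At higher control means the conversions lie closer together. That the gap exists follows from the text alone and does not depend on the simulation.

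This should be fixed before analysis. It is more than a missing detail, because a better-defined method is available at the planned sample size.

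**What to change.** In protocol D.9 (Analysis of Endpoints), the SAP's Analysis of Endpoints and the SAP's Methods for Dealing with Data Transformations, replace or qualify the clause with:

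> The 12-week RMDQ non-inferiority test and the time-averaged mixed-model non-inferiority test always use untransformed RMDQ against the 2-point margin. The 12-week 95% CI for the raw mean difference uses the unequal-variance (Welch) method whatever the normality checks show; the mixed model uses robust (sandwich) standard errors. Transformed or bootstrap analyses of RMDQ are sensitivity analyses only.

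Naming one interval method, with no trigger, avoids replacing one data-dependent choice with another. It should apply to both the intention-to-treat and per-protocol tests.

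The cost is a few sentences in each document, with no extra data or patients. In the scenarios examined, the Welch interval keeps power at 90–91% and error at 2.2–2.5% with 128 and 93 evaluable patients. The downside is a possible small loss of power against some transformed analyses if scores prove strongly skewed.
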